**Each sleep study night will consist of the following procedures:**

*Pre-sleep procedures.* Subjects will undergo a history and physical examination. They will report to the CRU at 4:00 PM and undergo anthropometric assessment including weight, height, neck, and waist circumference. At 5:30 PM, they will eat a standard dinner containing 30% fat, 50% carbohydrate, and 20% protein with kcal based upon the Mifflin-St Jeor formula. Two peripheral IVs (18 to 20 gauge) will be placed. All samples are obtained through the IV without disturbing the subject during sleep. Blood pressure will be checked at 6:30 PM, before administration of study drug. If systolic blood pressure is <90 or the heart rate is <50 then no drug will be administered. (In the event that this occurs, the study will still proceed so that CPAP and OSA nights can be compared and analyzed as a "no drug" group.) If blood pressure and heart rate are acceptable, propranolol LA 80 mg, or placebo (random order, crossover on study night 2 and 3) will be given. Participants and the investigators will be blinded to drug assignment.

*PSG setup.* On each study night from 10:30 PM until 6:30 AM, a PSG will be performed. The sleep study will include electroencephalography, electrooculography, oxygenation, respiratory effort, CPAP airflow, and transcutaneous CO2 monitoring. Respiratory effort will be measured by thoraco-abdominal movement assessed by mercury strain gauges. Surface electrodes will be placed at C3A2 and C3O1, a submental electrode, and left and right electro-oculogram will be used to stage sleep. Electrocardiograph (EKG) tracings will be recorded from three chest electrodes. Continuous measurement of oxygen saturation will be recorded using an ear oximeter (model No 472-1A, Hewlett Packard, Waltham, Mass). Transcutaneous CO2 will be monitored using a Radiometer TCM-4 device. Signals from the electroencephalograph, EKG, electromyogram, electrooculogram, respiratory strain gauge, ear oximeter and thermistors will be recorded on a computer with RemLogic software.

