**c. Blinding, including justification for blinding or not blinding the trial, if applicable.**

The subject and investigator will be blinded to whether they receive placebo or propranolol. This will control for the potential placebo effect of taking any medication before sleep. The investigator will unblind the drug assignment after the first 6 completed participants, so that adjustments to propranolol timing or dosage can be performed depending upon hemodynamic and metabolic effects. At that point, if the average OSA-induced FFA level is not reduced by at least 10%, the dosage of Inderal LA will be increased from 80 to 120 mg. The dosage will be reduced if there is any evidence of excessive bradycardia ( $>15\%$  reduction in heart rate) or hypotension (systolic BP $<90$ ). In addition, if the FFA nadir does not occur during the main sleep period, the timing of propranolol administration will be advanced or delayed as necessary. These adjustments will be made in collaboration with the research pharmacy. Regardless of whether the PI is blinded or unblinded, all data collection (sleep study, EndoPAT etc) will be performed in a blinded manner. For CPAP withdrawal nights, NDS will be used as a CPAP placebo. This will control for unintended effects of stopping CPAP such as anxiety before sleep.

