In this study, we will administer a single dose of long-acting (or “sustained release”) propranolol (Inderal® LA) 80 mg at 7:00 PM. This is the standard clinical starting dose for hypertension, and less than the nighttime dose of propranolol LA 120 mg used in a study of patients with bruxism[43]. The drug is coated with a semipermeable membrane to allow gradual absorption over a 12 hour period and a therapeutic window lasting ~24 hr. In a pharmacokinetic study, 160 mg of sustained release propranolol demonstrated gradual increase in plasma concentration to a peak ~6 hours after administration, then a gradual decline. By comparison, propranolol XL (Innopran XL) has a later onset of absorption, and a higher plasma peak and AUC than Inderal LA [44] which make it less desirable for this study. Propranolol LA 80 mg is less than the equivalent dosing of propranolol 40 T.I.D, the starting clinical dose for a variety of indications. For example, propranolol was used in the Beta Blocker Heart Attack Trial (BHAT, n=3,837), which administered 40 mg T.I.D, and later titrated up to 80 mg T.I.D [45]. In migraine headache, typical dosing is up to 160 mg propranolol daily in divided doses [46]. Propranolol LA at 160 mg daily is the target clinical dose in studies of angina pectoris, hypertension, and hyperthyroidism[42].

After interim analysis of the first 6 participants, we may adjust the dose and/or timing of propranolol based on its safety and efficacy, if necessary. For safety, the criterion is that on the propranolol night, the median heart rate during sleep should decrease by no more than 15% of basal heart rate as measured during the

placebo night. In addition, systolic blood pressure on the propranolol night should remain  $\geq 90$  mmHg. For efficacy, the decrease in overnight FFA levels by propranolol needs to be at least 10% as compared to the placebo night.

During CPAP withdrawal nights (both at home and in the lab) we will use NDS as a CPAP placebo. NDS may improve snoring but have no treatment value for OSA [38]. By including NDS as a placebo, we will avoid potential confounding such as anxiety caused by stopping CPAP.

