**7. Study Statistics**

- a. Primary outcome variable: Nocturnal FFA and glucose profile
- b. Secondary outcome variables: Morning EndoPAT, lipid panel. Sleep study parameters (e.g. total sleep time, latency, wake after sleep onset, sleep stages, AHI, oximetry, heart rate). Lipid flux data (rate of lipolysis and FFA turnover using stable isotope data; rate of fatty acid oxidation), DNA methylation profile.
- c. Statistical plan including sample size justification and interim data analysis.

**Comparisons between CPAP, [NDS + propranolol], and [NDS + Placebo]:** Primary outcome is comparison of metabolism and blood pressure for [NDS + propranolol] versus [NDS + placebo]. For metabolic parameters that are repeatedly measured during sleep (e.g. FFA, glucose) we will use mixed linear model analysis with experimental group as a fixed factor and subject ID as a random factor. Sleep physiology that is measured on a continuous basis (e.g. heart rate, AHI, SpO2) will be condensed into 30 minute bins to create a parallel data structure with metabolic parameters. We will then examine whether these sleep physiological metrics are dynamically associated with glucose/FFA level. For those parameters that are measured once per visit (e.g. RHI, lipid panel), we will compare using paired T-tests for within-subject comparisons between nights. A secondary outcome is whether CPAP and [NDS + propranolol] are similar, and this will be performed using a similar pairwise comparison. In addition, one way ANOVA will be used to ascertain whether there is a detectable difference across all three groups. Multiple regression will be used to examine associations between FFA, glucose, CPAP status, and drug adjusting for potential confounders such as diabetes, BMI, body fat (DEXA) and age. As an exploratory analysis, Pearson correlation matrices will be used to probe the interrelatedness of glucose, FFA, insulin, lipids, and sleep outcomes, followed by targeted multivariable regression. We plan an analysis of each subject's pulse rate and blood pressure after their PSG to determine whether beta blocker dosage or timing requires adjustment, which will expedite the ability to tailor the therapy if necessary.

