Sample size: In a preliminary study (n=6), Median individual heart rate during sleep \pm (SD) was 62.2 (9.2) with [OSA+placebo] and this decreased by 6.7 BPM with [OSA+propranolol]. To detect a 10% difference (reduction of 6.2 beats/min) at a power of 80% at a significance threshold of 0.05, using a one-tailed comparison, yields a sample size of 16 participants. Since we have already enrolled 5 subjects, we require 11 additional subjects. Assuming 20% dropout, we will enroll 14 additional subjects, a total of 19 participants.

Primary outcome: Median of continuously measured heart rate during sleep.

Secondary outcomes:

- augmentation index (normalized to 75 beats/min),
- heart rate variability metrics (HR standard deviation, min/max, 5th or 95th percentile)
- OSA severity (AHI, oximetry, event duration)
- sleep architecture (percent of each sleep stage during the night)
- Blood pressure
- metabolism (FFA, glucose, insulin).

Blinding:

As this is a double-blind study, above metrics will be calculated for each visit with only knowledge of visit number and not drug/placebo assignment. After these parameters have been derived, the research pharmacy will un-blind the biostatistician ([name]) and PI ([name]) to drug arm assignment to apply appropriate statistical tests, as described below.

Analysis:

For the primary analysis, we will derive summary metrics per night, per participant (i.e. median HR per night). Median heart rate per night will be compared between drug and placebo nights in a paired framework using paired student's T tests. Similar methods will be used to compare secondary outcomes. Some metrics will require additional derivation. For example, heart rate variation will be expressed as coefficients of variation, min/max and lower (5th) and upper (95th) percentiles, and visualized with Poincare plots as performed by collaborators at Johns Hopkins ².

Exploratory Analyses:

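### The protocol unblinds the investigator after six completed participants, on a comparison that is the SAP's primary outcome, while the SAP says the PI is unblinded only after the metrics are derived

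*Protocol*

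**What the plan says.** Protocol, Section 4 (procedures for each sleep study night) blinds both sides without exception: "Participants and the investigators will be blinded to drug assignment".

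Protocol, Section 4c (Blinding) makes an exception: "The investigator will unblind the drug assignment after the first 6 completed participants". The purpose is to review dose and timing against FFA, heart rate and blood pressure. The same paragraph limits the consequence: "Regardless of whether the PI is blinded or unblinded, all data collection (sleep study, EndoPAT etc) will be performed in a blinded manner".

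Protocol, Section 6a sets out what that look examines. Its heart-rate criterion is that, on the propranolol night, "the median heart rate during sleep should decrease by no more than 15% of basal heart rate", with the placebo night as the reference. It also compares overnight FFA between the two nights.

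Protocol, Section 7c adds a participant-level review: "We plan an analysis of each subject's pulse rate and blood pressure after their PSG". Its stated aim is to decide whether dose or timing should change. It names no reviewer and says nothing about the code.

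SAP, Blinding calls the study double-blind and says that the "above metrics will be calculated for each visit with only knowledge of visit number and not drug/placebo assignment". Then: "After these parameters have been derived, the research pharmacy will un-blind the biostatistician", together with the PI. The look after six participants is not mentioned.

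**The concern.** The documents disagree on when the PI learns drug assignment, and the early look includes the primary endpoint itself. A report that relied on the SAP's Blinding section would describe the PI as blind until the metrics existed, and the protocol does not provide for that.

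It matters because the PI has duties that the promise of blinded data collection does not cover. Under Post-test procedures in Section 4, the PI judges whether an inadequate night is repeated, and so which nights reach the analysis. Under Section 8c, the PI is the safety monitor and classifies the severity and attribution of adverse events. Knowing an assignment, or the interim effect, while making those decisions is what blinding is meant to prevent.

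**Working it through.** This is a comparison of texts. The documents give no figure for blinding that could be reproduced.

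**1. When the PI learns assignment**

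| Place | Who is unblinded | When |
|---|---|---|
| Protocol, Section 4, study-night procedures | Nobody | No exception given |
| Protocol, Section 4c | Investigator | After six completed participants |
| SAP, Blinding | Biostatistician and PI | After the metrics are derived |
| Protocol, Section 7c | Not stated | Review of each subject after PSG; no unblinding mentioned |

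There are two explicit unblinding points, and they differ. The study-night text agrees with neither, because it allows no exception.

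**2. What the early look exposes**

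- Section 6a compares median sleep heart rate, drug night against placebo night. The SAP's primary outcome is median sleep heart rate, and its primary analysis is the paired comparison of the same two nights.
- Section 6a also compares overnight FFA. FFA is a primary outcome in Section 7a of the protocol and a secondary outcome in the SAP.

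**3. Signs that results by condition were available early**

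- The sample-size text in Section 7c gives mean nocturnal FFA for each condition in 3 patients who had completed their visits. That is fewer than the six after which Section 4c opens the code.
- The SAP's sample-size text gives a fall of 6.7 BPM on propranolol in n=6.
- The SAP counts 5 subjects as already enrolled toward its 16. The documents do not say whether the 3, the 5, the n=6 and the six in Section 4c overlap, or who held the code for the figures on the 3 and the n=6.

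**4. Whether the Section 7c review needs the code**

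- A systolic pressure below 90 is an absolute limit and can be checked blind.
- The 15% heart-rate criterion compares two named nights, so applying it to one person needs the assignment. With one drug night and one placebo night, identifying one identifies the other.
- Section 6a gives that criterion for the look after six participants, and Section 7c does not say that it applies to each person.
- Section 4f says each participant receives propranolol once, so it is also unclear whose dose or timing this review would change.

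Section 7c is therefore unclear, and it is not a stated third unblinding.

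**5. Share of the sample**

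- 6/16 = 37.5% of the SAP's required participants; 6/19 = 31.6% of its planned enrolment.
- 5/16 = 31.3% and 5/19 = 26.3% if only the 5 already enrolled are affected.
- 6/30 = 20% and 6/36 = 16.7% on the protocol's enrolment and consent targets.

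**6. Precision of an analysis without them**

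The standard error of a paired mean difference is s/√n. With s unchanged, going from 16 to 10 multiplies it by √(16/10) = 1.26, and going from 16 to 11 by √(16/11) = 1.21.

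**The case against.** The best defence is that the two rules can both be met. If the metrics of the first six were derived blind before their code was opened, the SAP's sequence was kept for them. Section 4c also discloses the look with its reason, and keeps data collection blinded. The six had completed their nights, so decisions on repeating those nights were largely past, and most of their adverse events would already have been assessed. The circumstances for a repeat are listed, and a median of continuously recorded heart rate leaves little room for observer judgement.

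Much of this stands, and it makes large bias from the stated look less likely. It does not remove the conflict. The SAP neither mentions the look nor says that derivation came first. Even if it did, the PI would carry the interim result on the primary outcome into decisions about later participants, and the unqualified statement in the study-night procedures would still be wrong.

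A reader might infer more: that there are three unblinding points, that the Section 7c review exposes every participant, or that the trial is not double-blind at all. The documents do not support these. Section 7c mentions neither code nor assignment. Nothing says that participants are told their assignment, or that assignments after the sixth are opened early. Counting everyone as exposed rests on an inference from Section 7c alone.

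**Conclusion.** The conflict is real but limited. As the documents stand, the SAP's blinding statement does not hold for the PI for the early participants, and the comparison opened early is the primary one. If all six belong to the SAP's sample, they are 37.5% of 16 or 31.6% of 19; membership is not established, since the SAP speaks of 5 already enrolled. Blinding of participants and of data collection is not shown to fail.

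Two assumptions carry this: that the unblinding in Section 4c took place as planned, and that the first six did not have their metrics derived blind beforehand. The second is not documented either way. Neither the direction nor the size of any bias can be derived from the documents.

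**What to change.** 1. Reconcile the protocol's study-night procedures and Sections 4c, 6a and 7c with the SAP's Blinding section, so that they agree on who sees the code and when. The dose and timing rules in 4c, 6a and 7c must be reconciled in the same step; no view is taken here on which is right.
2. Limit code access for any dose or timing review to the research pharmacy and the biostatistician, and say so in the SAP, which at present opens the code to the biostatistician only after derivation. State how the Section 7c review is done without assignment, or who does it with assignment.
3. Keep the PI, and staff who derive metrics, decide on repeat nights or attribute adverse events, blind until all nights are scored and locked.
4. Correct the SAP's Blinding section to state who was unblinded, when and for which participants. It should cover the 3 patients with FFA by condition and the n=6 with heart rate by condition, and say which of them enter the primary analysis.
5. Add a sensitivity analysis of the primary outcome without the participants already unblinded.

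The cost is wording changes and one extra analysis, whose standard error would be about 21% to 26% larger if 5 or 6 of 16 are left out. The trial also has to accept a less favourable description of its blinding. What the PI has already seen cannot be undone, so for those participants the remedy is disclosure and the sensitivity analysis.

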**Study overview:** There are a total of 4 study visits. The first visit is a consent, screening, and randomization visit. After consent, a screening EKG will be performed to exclude rhythm or conduction abnormalities and a urine pregnancy test to exclude pregnancy in potentially pregnant females. (If the participant has had a clinical EKG or EKG report in the last year that does not indicate any conduction disorders listed in the exclusion criteria, the screening EKG may be deferred.) A point of care screening test for hemoglobin will also be performed to exclude pre-existing anemia. Patients with a hemoglobin < 10 g/dL are ineligible for this study. They will be provided with ClearPassage® NDS to use at home during CPAP withdrawal nights.

Thereafter, there are 3 overnight visits to the CRU in random order. This protocol compares nocturnal metabolism in treated OSA (CPAP), untreated OSA (NDS), and beta-blocked OSA (NDS) in the same subject. OSA nights are performed in the lab after using NDS instead of CPAP for 2 nights at home.

**Covid-19 screening:** We will screen participants before their arrival for their each sleep study with a Covid-19 test. A negative screen within 72 hours of the CPAP visit will be needed prior to admission for the CPAP study visit.

During each OSA visit, propranolol or placebo is taken in the evening, in random order. Frequent blood sampling is performed throughout the visit. In the morning, DEXA (only 1 DEXA needed for entire study) is performed. We are targeting 1 week between visits, but will allow flexibility in scheduling patients unable to schedule 3 consecutive visits exactly 1 week apart; in this scenario we will allow a duration of  $\geq$  4 days or  $\leq$  3 weeks between visits. Each visit we will also administer stable isotopes to measure detailed lipid metabolism.

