**Post-test procedures:** To minimize the impact of sleep loss on driving safety, subjects are asked to either (1) arrange for an alternate means of transportation home (this is mentioned on the consent or to (2) sleep as needed for up to 4 additional hours before discharge. Repeat sleep tests may be requested from the subject under the following circumstances: (1) A technical problem with data acquisition including PSG lead failure/artifacts, incomplete blood collection from IV insertion or maintenance problems. (2) Poor sleep efficiency <50% of time in bed. (3) inadequate resumption of OSA (AHI>15) or its effective treatment with CPAP (AHI<10). If sleep studies meet these criteria and a repeat test is deemed necessary by the PI, then the repeat testing will be scheduled at least 1 week following the inadequate study.

[figure not shown]

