An exploratory aim of this study is to examine effects of CPAP withdrawal on peripheral blood mononuclear cell (PBMC) gene expression. We will utilize real-time polymerase chain reaction (RT-PCR) arrays (Qiagen MAP Kinase RT2 Profiler and Human Toll-Like Receptor (TLR) Signaling Pathway RT2 Profiler PCR Arrays, Qiagen, Valencia, CA) to characterize gene changes that result from nocturnal hypoxemia.

**Sample size:** In our preliminary data from 3 patients who have completed their study visits, FFA levels increased with OSA (CPAP withdrawal), and propranolol abolished this response. The mean nocturnal FFA level on CPAP, [OSA + placebo], and [OSA + propranolol] nights was  $0.413 \pm 0.107$ ,  $0.447 \pm 0.084$  and  $0.313 \pm 0.067$  mmol/L respectively. We base our sample size on the ability to detect an effect of propranolol on FFA levels during sleep. The mean difference of FFA between [OSA + placebo] and [OSA + propranolol] nights was  $0.133 \pm 0.076$  mmol/L (mean  $\pm$  standard deviation). This yields a large effect size (Cohen's  $d = 1.673$ ). However, we anticipate a smaller effect size with ongoing enrollment. In addition, our pilot data consisted only of men, and we do not have data from which to estimate an effect size for women. We estimate a more modest difference in means of 0.06. This yields a Cohen's  $d = 0.79$ . To detect a difference at 90% power at a significance level of 0.05 requires a sample size of 15 subjects. We will compare both sexes, so we will target an enrollment of 30 subjects. To account for 20% data loss from technical problems (IV failure, hemolysis, poor sleep efficiency) we will consent 36 subjects.

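### Consenting 36 does not leave 30 with usable data after the protocol's own 20% loss, and it counts consents rather than participants who pass screening (a minor sizing slip)

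*Protocol*

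**What the plan says.** The sample-size paragraph of protocol section 7c has three steps.

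- Base number: "To detect a difference at 90% power at a significance level of 0.05 requires a sample size of 15 subjects". It assumes a difference in nocturnal FFA of 0.06 mmol/L ("We estimate a more modest difference in means of 0.06") and a standard deviation of the paired difference of 0.076 mmol/L from three pilot patients, giving a stated Cohen's d of 0.79.
- Doubling: "We will compare both sexes, so we will target an enrollment of 30 subjects".
- Loss allowance: "To account for 20% data loss from technical problems (IV failure, hemolysis, poor sleep efficiency) we will consent 36 subjects". No inflation formula is shown.

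Eligibility is settled partly after consent. The study overview in protocol section 4 says: "After consent, a screening EKG will be performed to exclude rhythm or conduction abnormalities". The pregnancy test and the point-of-care hemoglobin check come at the same stage. The blood-pressure and heart-rate limits at the screening visit are in section 5 (exclusion criterion 1e).

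Section 4, under post-test procedures, also provides for repeating inadequate nights: "Repeat sleep tests may be requested from the subject under the following circumstances". The listed circumstances include technical failure, incomplete blood collection because of IV problems, and poor sleep efficiency.

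**The concern.** An allowance for loss should return the required number once the loss has happened. Multiplying by 1.2 does not do this for a 20% loss, because the 20% is then taken from the larger starting number. The protocol's own rate therefore gives fewer than the 30 it aims for.

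The denominator is a second problem. The named causes of loss (IV failure, hemolysis, poor sleep efficiency) arise on study nights, but the 36 are counted at consent. Anyone excluded at screening is lost from the 36 before the 20% begins to apply, and nothing is set aside for that.

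At stake are one or two evaluable participants from the formula, plus an unknown number from screening. This bears mainly on the per-sex numbers that justify the doubling.

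**Working it through.** **Inputs (protocol section 7c).** Target 30 = 2 × 15; loss 20%; consent target 36; d = 0.06/0.076 = 0.789, stated as 0.79; significance level 0.05, with sidedness not stated.

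**1. Reproduce the plan's figure.** 30 × (1 + 0.20) = 36, exactly the stated number.

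**2. Apply the stated loss to 36.** 36 × (1 − 0.20) = 28.8 expected with usable data.

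**3. Invert the loss.** 30/(1 − 0.20) = 37.5, rounded up to 38. Check: 38 × 0.8 = 30.4.

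**4. Loss rate at which 36 is enough.** 1 − 30/36 = 16.7%.

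**5. Chance of reaching 30.** With an independent 20% loss per participant (a binomial assumption), the probability of at least 30 evaluable is 0.40 from 36 and 0.66 from 38.

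**6. Effect on power.** Paired t test, noncentral t distribution with n − 1 degrees of freedom and noncentrality d√n, d = 0.79. For example, 0.79 × √15 = 3.06 and 0.79 × √14 = 2.96. An equal sex split gives 28.8/2 = 14.4 per sex, so 14 is compared with 15.

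| n | One-sided | Two-sided |
|---|---|---|
| 15 (per sex, as intended) | 89.7% | 81.2% |
| 14 (per sex, after a 20% loss from 36) | 87.5% | 78.0% |
| 30 (pooled, as intended) | 99.5% | 98.7% |
| 28 (pooled, after a 20% loss from 36) | 99.2% | 98.1% |

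Per sex the drop is 2.2 points one-sided or 3.2 points two-sided. Pooled, it is 0.3 or 0.6 points.

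**7. Screening.** The documents give no screen-failure rate. Purely as an illustration, 2 to 4 failures among 36 would leave 34 × 0.8 = 27.2 down to 32 × 0.8 = 25.6 evaluable. So 28.8 is the expected number only if everyone who consents passes screening.

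**The case against.** The strongest reply is that this is a two-subject slip inside a calculation with far larger uncertainty, since the standard deviation comes from three men. Several parts of the reply stand.

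- **The 30 is called a target enrollment, not an evaluable number.** Reading it as evaluable is an inference. It is a reasonable one: 30 is twice the number required for power, and adding participants for lost data makes sense only if 30 is the number with data.
- **The 90% power statement attaches to 15, not to 30.** A reader might infer that the main drug-versus-placebo comparison is left short. The documents do not support that: 28 to 29 pooled is nearly twice the stated requirement.
- **No sex split is stated.** The figure of 14 per sex rests on an equal split and is not a consequence of the plan as written.
- **Repeat nights may recover some losses.** They cover at least IV problems and poor sleep efficiency, two of the three named causes. They are at the investigator's discretion, and the protocol does not say whether the 20% is before or after repeats. They do nothing for screening exclusions.
- **Three patients had already completed.** If they count toward the 36, which is not stated, the expected number is 3 + 33 × 0.8 = 29.4.
- **Some screening may not cost participants.** A recent clinical EKG may replace the screening one, and no failure rate is available. The gap in the allowance is real, but its size is unknown.

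A reader might also infer that the SAP inflates correctly and so contradicts the protocol. It says: "Assuming 20% dropout, we will enroll 14 additional subjects, a total of 19 participants". But 11/0.8 = 13.75 and 11 × 1.2 = 13.2 both round up to 14. The SAP shows no formula, and its figure fits either method, so it is no evidence of a different one.

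**Conclusion.** The point holds as a minor correction. At the protocol's own 20% rate, 36 gives about 28.8 participants with usable data. The number that corresponds to 30 is 38, two more than stated. The 36 also counts consents, while the allowance covers only technical loss after screening.

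The cost from the formula alone is 2 to 3 points of power per sex and under one point pooled. This rests on reading 30 as the number with usable data, an equal sex split for the per-sex figures, d = 0.79, and losses not recovered by repeat nights. Screening failures would add to the shortfall by an amount the documents do not allow one to estimate.

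Two larger matters are separate from this one and are not resolved by correcting 36. At d = 0.79, 15 subjects give about 90% power only one-sided (81.2% two-sided). The SAP of April 2023 sizes the trial on heart rate, with a total of 19.

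**What to change.** In protocol section 7c, restate the last step of the sample-size paragraph in one of two ways:

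- 36 participants passing screening are expected to give about 28 to 29 evaluable at a 20% loss, with the power that follows; or
- 38 participants passing screening are the number that corresponds to 30 evaluable.

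In either case, state that the 20% is counted from those who pass screening, and whether it is before or after repeat nights. If a consent target is still wanted, give the assumed screen-failure rate beside it.

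The cost is a sentence or two. The first option makes the stated evaluable number slightly less favourable; the second adds two participants beyond screening. No study procedure changes.
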